9.2.03 Pregnancy Test

A urine pregnancy test will be obtained at the study site for female subjects of childbearing potential at Screening and weeks 0, 4, 8, 12, 16, 20, 24, 28, 32, 36, 40, 44, 48, 52, and at early termination when applicable.

10 EVALUATIONS BY VISIT

See Appendix 1 for Evaluation Schedule.

10.01 Visit 1 (Screening)

1. Verify that patient meets all inclusion criteria and exclusion criteria
2. Informed Consent/HIPAA Authorization/UCSF Experimental Subject's Bill of Rights - Prior to any testing under this protocol, including screening and evaluations, written

informed consent will be obtained from the subject by the investigators. The background of the proposed study, benefits, and risks of procedures will be explained to the subject. Informed consent will be obtained after the subject has a chance to ask questions. A copy of the signed and dated informed consent, HIPAA Authorization, and UCSF Experimental Subject's Bill of Rights will be given to the subject. At the time of written informed consent, subjects will be given the name and phone number of personnel at the study site that can be called in the event of an emergency or to report any medical symptoms or untoward medical occurrence that is of concern to the subject.

3. Obtain patient demographic information
4. Medical history – a full medical history including all medications
5. Atopic dermatitis treatment history – past treatments with special focus on any treatment during the last 30 days
6. Physical examination
 - a. Height and weight
 - b. Vital signs: temperature, blood pressure, pulse, and respiratory rate
 - c. Comprehensive physical exam
 - d. Eczema Area and Severity Index (EASI)
 - e. Investigator's Global Assessment (IGA)
7. Clinical Laboratories:
 - a. Hematology
 - b. Chemistry
8. Urine Pregnancy Test (if applicable)

10.02 Visit 2 (Week 0)

1. Review inclusion and exclusion criteria
2. Brief interim medical history
3. Review concomitant medications
4. Physical examination
 - a. Height and weight
 - b. Vital signs: temperature, blood pressure, pulse, and respiratory rate
 - c. Eczema Area and Severity Index (EASI)
 - d. Investigator's Global Assessment (IGA)
5. Urine pregnancy test (if applicable)
6. Full-body photography (excluding face)
7. Quality of Life Measures:
 - a. WPAI
 - b. PGWB
 - c. DLQI

8. Other patient questionnaires:
 - a. Itch Numerical Rating Scale
 - b. Pain Numerical Rating Scale
 - c. Pittsburgh Sleep Quality Assessment (PSQI)
9. Study drug injection
10. Dispense study medication and dosing diaries for home use
11. Sign out video recording device and instruct patients on proper use

10.03 Visit 3 (Week 4)

1. Brief interim medical history
2. Review adverse events
3. Reconcile concomitant medications
4. Study staff download patient videos
5. Study staff collect, review, and record home study drugs administration
6. Physical examination
 - a. Height and weight
 - b. Vital signs: temperature, blood pressure, pulse, and respiratory rate
 - c. Eczema Area and Severity Index (EASI)
 - d. Investigator's Global Assessment (IGA)
7. Urine pregnancy test (if applicable)
8. Quality of Life Measures:
 - a. WPAI
 - b. PGWB
 - c. DLQI
9. Other patient questionnaires:
 - a. Itch Numerical Rating Scale
 - b. Pain Numerical Rating Scale
 - c. Pittsburgh Sleep Quality Assessment (PSQI)
10. Study drug injection
11. Dispense study drug and dosing diary for home use

10.04 Visit 4 (Week 8)

1. Brief interim medical history
2. Review adverse events
3. Reconcile concomitant medications

4. Study staff download patient videos
5. Study staff collect, review, and record home study drugs administration
6. Physical examination
 - a. Height and weight
 - b. Vital signs: temperature, blood pressure, pulse, and respiratory rate
 - c. Eczema Area and Severity Index (EASI)
 - d. Investigator's Global Assessment (IGA)
7. Urine pregnancy test (if applicable)
8. Quality of Life Measures:
 - a. WPAI
 - b. PGWB
 - c. DLQI
9. Other patient questionnaires:
 - a. Itch Numerical Rating Scale
 - b. Pain Numerical Rating Scale
 - c. Pittsburgh Sleep Quality Assessment (PSQI)
10. Study drug injection
11. Dispense study drug and dosing diary for home use

10.05 Visit 5 (Week 12)

1. Brief interim medical history
2. Review adverse events
3. Reconcile concomitant medications
4. Study staff download patient videos
5. Study staff collect, review, and record home study drugs administration
6. Physical examination
 - a. Height and weight
 - b. Vital signs: temperature, blood pressure, pulse, and respiratory rate
 - c. Eczema Area and Severity Index (EASI)
 - d. Investigator's Global Assessment (IGA)
7. Urine pregnancy test (if applicable)
8. Quality of Life Measures:
 - a. WPAI
 - b. PGWB
 - c. DLQI

9. Other patient questionnaires:
 - a. Itch Numerical Rating Scale
 - b. Pain Numerical Rating Scale
 - c. Pittsburgh Sleep Quality Assessment (PSQI)
10. Study drug injection
11. Dispense study drug and dosing diary for home use

10.06 Visit 6 (Week 16)

1. Brief interim medical history
2. Review adverse events
3. Reconcile concomitant medications
4. Study staff download patient videos
5. Study staff collect, review, and record home study drugs administration
6. Physical examination
 - a. Height and weight
 - b. Vital signs: temperature, blood pressure, pulse, and respiratory rate
 - c. Eczema Area and Severity Index (EASI)
 - d. Investigator's Global Assessment (IGA)
7. Urine pregnancy test (if applicable)
8. Full-body photography (excluding face)
9. Quality of Life Measures:
 - a. WPAI
 - b. PGWB
 - c. DLQI
10. Other patient questionnaires:
 - a. Itch Numerical Rating Scale
 - b. Pain Numerical Rating Scale
 - c. Pittsburgh Sleep Quality Assessment (PSQI)
11. Study drug injection
12. Dispense study drug and dosing diary for home use

10.07 Visit 7 (Week 20)

1. Brief interim medical history
2. Review adverse events
3. Reconcile concomitant medications

4. Study staff download patient videos
5. Study staff collect, review, and record home study drugs administration
6. Physical examination
 - a. Height and weight
 - b. Vital signs: temperature, blood pressure, pulse, and respiratory rate
 - c. Eczema Area and Severity Index (EASI)
 - d. Investigator's Global Assessment (IGA)
7. Urine pregnancy test (if applicable)
8. Quality of Life Measures:
 - a. WPAI
 - b. PGWB
 - c. DLQI
9. Other patient questionnaires:
 - a. Itch Numerical Rating Scale
 - b. Pain Numerical Rating Scale
 - c. Pittsburgh Sleep Quality Assessment (PSQI)
10. Study drug injection
11. Dispense study drug and dosing diary for home use

10.08 Visit 8 (Week 24)

1. Brief interim medical history
2. Review adverse events
3. Reconcile concomitant medications
4. Study staff download patient videos
5. Study staff collect, review, and record home study drugs administration
6. Physical examination
 - a. Height and weight
 - b. Vital signs: temperature, blood pressure, pulse, and respiratory rate
 - c. Eczema Area and Severity Index (EASI)
 - d. Investigator's Global Assessment (IGA)
7. Urine pregnancy test (if applicable)
8. Full-body photography (excluding face)
9. Quality of Life Measures:
 - a. WPAI
 - b. PGWB

- c. DLQI
- 10. Other patient questionnaires:
 - a. Itch Numerical Rating Scale
 - b. Pain Numerical Rating Scale
 - c. Pittsburgh Sleep Quality Assessment (PSQI)
- 11. Study drug injection
- 12. Dispense study drug and dosing diary for home use

10.09 Visit 9 (Week 28)

- 1. Brief interim medical history
- 2. Review adverse events
- 3. Reconcile concomitant medications
- 4. Study staff download patient videos
- 5. Study staff collect, review, and record home study drugs administration
- 6. Physical examination
 - a. Height and weight
 - b. Vital signs: temperature, blood pressure, pulse, and respiratory rate
 - c. Eczema Area and Severity Index (EASI)
 - d. Investigator's Global Assessment (IGA)
- 7. Urine pregnancy test (if applicable)
- 8. Quality of Life Measures:
 - a. WPAI
 - b. PGWB
 - c. DLQI
- 9. Other patient questionnaires:
 - a. Itch Numerical Rating Scale
 - b. Pain Numerical Rating Scale
 - c. Pittsburgh Sleep Quality Assessment (PSQI)
- 10. Study drug injection
- 11. Dispense study drug and dosing diary for home use

10.10 Visit 10 (Week 32)

- 1. Brief interim medical history
- 2. Review adverse events
- 3. Reconcile concomitant medications

4. Study staff download patient videos
5. Study staff collect, review, and record home study drugs administration
6. Physical examination
 - a. Height and weight
 - b. Vital signs: temperature, blood pressure, pulse, and respiratory rate
 - c. Eczema Area and Severity Index (EASI)
 - d. Investigator's Global Assessment (IGA)
7. Urine pregnancy test (if applicable)
8. Quality of Life Measures:
 - a. WPAI
 - b. PGWB
 - c. DLQI
9. Other patient questionnaires:
 - a. Itch Numerical Rating Scale
 - b. Pain Numerical Rating Scale
 - c. Pittsburgh Sleep Quality Assessment (PSQI)
10. Study drug injection
11. Dispense study drug and dosing diary for home use

10.11 Visit 11 (Week 36)

1. Brief interim medical history
2. Review adverse events
3. Reconcile concomitant medications
4. Study staff download patient videos
5. Study staff collect, review, and record home study drugs administration
6. Physical examination
 - a. Height and weight
 - b. Vital signs: temperature, blood pressure, pulse, and respiratory rate
 - c. Eczema Area and Severity Index (EASI)
 - d. Investigator's Global Assessment (IGA)
7. Urine pregnancy test (if applicable)
8. Quality of Life Measures:
 - a. WPAI
 - b. PGWB
 - c. DLQI

9. Other patient questionnaires:
 - a. Itch Numerical Rating Scale
 - b. Pain Numerical Rating Scale
 - c. Pittsburgh Sleep Quality Assessment (PSQI)
10. Study drug injection
11. Dispense study drug and dosing diary for home use

10.12 Visit 12 (Week 40)

1. Brief interim medical history
2. Review adverse events
3. Reconcile concomitant medications
4. Study staff download patient videos
5. Study staff collect, review, and record home study drugs administration
6. Physical examination
 - a. Height and weight
 - b. Vital signs: temperature, blood pressure, pulse, and respiratory rate
 - c. Eczema Area and Severity Index (EASI)
 - d. Investigator's Global Assessment (IGA)
7. Urine pregnancy test (if applicable)
8. Quality of Life Measures:
 - a. WPAI
 - b. PGWB
 - c. DLQI
9. Other patient questionnaires:
 - a. Itch Numerical Rating Scale
 - b. Pain Numerical Rating Scale
 - c. Pittsburgh Sleep Quality Assessment (PSQI)
10. Study drug injection
11. Dispense study drug and dosing diary for home use

10.13 Visit 13 (Week 44)

1. Brief interim medical history
2. Review adverse events
3. Reconcile concomitant medications
4. Study staff download patient videos

5. Study staff collect, review, and record home study drugs administration
6. Physical examination
 - a. Height and weight
 - b. Vital signs: temperature, blood pressure, pulse, and respiratory rate
 - c. Eczema Area and Severity Index (EASI)
 - d. Investigator's Global Assessment (IGA)
7. Urine pregnancy test (if applicable)
8. Quality of Life Measures:
 - a. WPAI
 - b. PGWB
 - c. DLQI
9. Other patient questionnaires:
 - a. Itch Numerical Rating Scale
 - b. Pain Numerical Rating Scale
 - c. Pittsburgh Sleep Quality Assessment (PSQI)
10. Study drug injection
11. Dispense study drug and dosing diary for home use

10.14 Visit 14 (Week 48)

1. Brief interim medical history
2. Review adverse events
3. Reconcile concomitant medications
4. Study staff download patient videos
5. Study staff collect, review, and record home study drugs administration
6. Physical examination
 - a. Height and weight
 - b. Vital signs: temperature, blood pressure, pulse, and respiratory rate
 - c. Eczema Area and Severity Index (EASI)
 - d. Investigator's Global Assessment (IGA)
7. Urine pregnancy test (if applicable)
8. Quality of Life Measures:
 - a. WPAI
 - b. PGWB
 - c. DLQI
9. Other patient questionnaires:

- a. Itch Numerical Rating Scale
- b. Pain Numerical Rating Scale
- c. Pittsburgh Sleep Quality Assessment (PSQI)

10. Study drug injection
11. Dispense study drug and dosing diary for home use

10.15 Visit 15 (Week 52)

1. Brief interim medical history
2. Review adverse events
3. Reconcile concomitant medications
4. Study staff download patient videos
5. Study staff collect, review, and record home study drugs administration
6. Physical examination
 - a. Height and weight
 - b. Vital signs: temperature, blood pressure, pulse, and respiratory rate
 - c. Eczema Area and Severity Index (EASI)
 - d. Investigator's Global Assessment (IGA)
7. Urine pregnancy test (if applicable)
8. Full-body photography (excluding face)
9. Quality of Life Measures:
 - a. WPAI
 - b. PGWB
 - c. DLQI
10. Other patient questionnaires:
 - a. Itch Numerical Rating Scale
 - b. Pain Numerical Rating Scale
 - c. Pittsburgh Sleep Quality Assessment (PSQI)

10.16 Early termination

1. Brief interim medical history
2. Review adverse events
3. Reconcile concomitant medications
4. Study staff download patient videos
5. Study staff collect, review, and record home study drugs administration

6. Physical examination
 - a. Height and weight
 - b. Vital signs: temperature, blood pressure, pulse, and respiratory rate
 - c. Eczema Area and Severity Index (EASI)
 - d. Investigator's Global Assessment (IGA)
7. Urine pregnancy test (if applicable)
8. Full-body photography (excluding face)
9. Quality of Life Measures:
 - a. WPAI
 - b. PGWB
 - c. DLQI
10. Other patient questionnaires:
 - a. Itch Numerical Rating Scale
 - b. Pain Numerical Rating Scale
 - c. Pittsburgh Sleep Quality Assessment (PSQI)

11 ADVERSE EXPERIENCE REPORTING AND DOCUMENTATION

11.1 Adverse Events

Definition of an AE: Any untoward medical occurrence in a subject administered a pharmaceutical product that does not necessarily have a causal relationship with the treatment. An AE can therefore be any unfavorable and unintended sign (including an abnormal laboratory finding), symptom, or disease temporally associated with the use of a medicinal (investigational) product, whether or not considered related to the investigational medicinal product.

Investigational Medicinal Product (IMP) includes the drug under evaluation and the comparator drug(s) if specified as part of the research objective, given at any time during the study. Medical conditions/diseases present before starting the drug of interest are only considered adverse events if they worsen after starting the drug of interest.

The occurrence of adverse events will be sought by non-directive questioning of the patient at each visit during the study. Adverse events also may be detected when they are volunteered by the patient during or between visits or through physical examination, laboratory test, or other assessments. All adverse events will be recorded in the study database including the following information:

1. the severity grade (mild, moderate, severe)
2. its relationship to the drug(s) of interest (suspected/not suspected)
3. its duration (start and end dates or if continuing at final exam)
4. whether it constitutes a serious adverse event (SAE)

AE Severity

The National Cancer Institute's Common Terminology Criteria for Adverse Events (CTCAE) Version 3.0 should be used to assess and grade AE severity, including laboratory abnormalities judged to be clinically significant. The modified criteria can be found in the study manual. If the experience is not covered in the modified criteria, the guidelines shown in **Error! Reference source not found.** below should be used to grade severity. It should be pointed out that the term "severe" is a measure of intensity and that a severe AE is not necessarily serious.

Table 1. AE Severity Grading

Severity (Toxicity Grade)	Description
Mild (1)	Transient or mild discomfort; no limitation in activity; no medical intervention or therapy required. The subject may be aware of the sign or symptom but tolerates it reasonably well.
Moderate (2)	Mild to moderate limitation in activity, no or minimal medical intervention/therapy required.
Severe (3)	Marked limitation in activity, medical intervention/therapy required, hospitalizations possible.
Life-threatening (4)	The subject is at risk of death due to the adverse experience as it occurred. This does not refer to an experience that hypothetically might have caused death if it were more severe.

Table 2. AE Relationship to Study Drug

Relationship to Drug	Comment
Definitely	Previously known toxicity of agent; or an event that follows a reasonable temporal sequence from administration of the drug; that follows a known or expected response pattern to the suspected drug; that is confirmed by stopping or reducing the dosage of the drug; and that is not explained by any other reasonable hypothesis.
Probably	An event that follows a reasonable temporal sequence from administration of the drug; that follows a known or expected response pattern to the suspected drug; that is confirmed by stopping or reducing the dosage of the drug; and that is unlikely to be explained by the known characteristics of the subject's clinical state or by other interventions.
Possibly	An event that follows a reasonable temporal sequence from administration of the drug; that follows a known or expected response pattern to that suspected drug; but that could readily have been produced by a number of other factors.

Unrelated	An event that can be determined with certainty to have no relationship to the study drug.
-----------	---

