14.2 Analysis of Secondary Endpoints

1. Efficacy Endpoints

- a.** EASI and IGA scores at week 16 will be compared to baseline.

2. Safety Endpoints

- a.** Safety will be evaluated by tabulation of adverse events (AEs), including any Serious Adverse Events (SAEs) within treatment groups. All AEs occurring during the study will be recorded. Descriptions of adverse events will include the date of onset, the date the adverse event ended, the severity of the adverse event, and the outcome. All reported adverse events will be summarized by the number of subjects reporting adverse events, body system, severity, seriousness, and relationship to study treatment.

3. Analysis of Other Endpoints

- a.** Other variables may be analyzed and presented descriptively. The methods to be used will include (but are not limited to) parametric and nonparametric analysis, means, standard deviations, frequency counts and graphs, as appropriate.
- b.** Video footage of patient experiences will be compiled at the end of the study. The compiled video footage will subsequently be watched and analyzed to further understand the experiences of atopic dermatitis patients, and how undergoing dupilumab treatment alters these patients' experiences and attitudes with their skin disease.

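### AE severity is recorded on three levels but graded on four, so the planned severity summary cannot separate life-threatening from severe events

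*Combined protocol and SAP*

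**What the plan says.** Section 11.1 lists what is recorded in the study database for every adverse event. Item 1 is "the severity grade (mild, moderate, severe"), and item 4 is whether the event is serious.

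For grading, the same section says that "Common Terminology Criteria for Adverse Events (CTCAE) Version 3.0 should be used to assess and grade AE severity", with modified criteria kept in a study manual that is not part of these documents. Table 1 is a fallback, used "If the experience is not covered in the modified criteria". It has four rows:

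- The lowest row, grade 1 or mild, is worded "Transient or mild discomfort; no limitation in activity; no medical intervention or therapy required".
- The next row up, grade 2 or moderate, is worded "Mild to moderate limitation in activity, no or minimal medical intervention/therapy required".
- The third row, grade 3 or severe, is worded "Marked limitation in activity, medical intervention/therapy required, hospitalizations possible".
- The top row, grade 4, is for life-threatening events and is worded "The subject is at risk of death due to the adverse experience as it occurred".

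Section 9.1.06 says that the CRF captures severity or grade, without giving the levels. Section 14.2 plans the output: "All reported adverse events will be summarized by the number of subjects reporting adverse events, body system, severity, seriousness, and relationship to study treatment". Safety is the fourth secondary endpoint in Section 5.2.

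**The concern.** A grading scale and the field that stores it should have the same levels. Here the plan can assign a grade that its own list of recorded values does not contain. The loss happens at data entry. Section 14 leaves the detailed SAP to be written before the final analysis, but an SAP can only tabulate what was collected. If grade 4 events have been stored as severe, separating them later means going back to SAE reports or source documents.

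The second issue is inside Table 1. Each of the first three rows pairs a degree of activity limitation with a degree of intervention. The two need not move together, and nothing says which one governs when they differ. Two assessors could then grade the same event differently. What is at stake is the consistency and resolution of one safety table.

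**Working it through.** The plan states no figure to reproduce. The check is a comparison of levels, followed by a count of combinations.

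**Step 1: recorded levels against grading levels.**

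- Recorded list (Section 11.1, item 1): mild, moderate, severe = 3 levels.
- Table 1 (Section 11.1): grades 1, 2, 3, 4 = 4 levels.
- Difference: 4 − 3 = 1 level, life-threatening, with no recorded value and no mapping rule.

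Section 9.1.06 does not settle this, because it gives no levels, and no CRF code list is in the documents.

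**Step 2: whether another recorded item restores the lost level.** Section 11.2 gives six criteria for an SAE: death, life-threatening, hospitalization, disability, congenital anomaly, and other significant medical event. Item 4 of the 11.1 list is yes/no. A positive flag therefore says that at least one of six criteria was met, not which one. A life-threatening event stored as severe and serious looks the same in these two fields as a severe event that led to hospitalization.

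**Step 3: coverage of Table 1, grades 1 to 3.** Limitation is taken at three levels (none, mild to moderate, marked) and intervention at three (none, minimal, more than minimal). This gives 3 × 3 = 9 combinations. Each row is read as requiring both of its parts.

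| Limitation | No intervention | Minimal | More than minimal |
|---|---|---|---|
| None | Mild | no grade | no grade |
| Mild to moderate | Moderate | Moderate | no grade |
| Marked | no grade | Severe, if minimal counts as required | Severe |

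- If minimal therapy counts as required for grade 3: graded 1 + 2 + 2 = 5, ungraded 9 − 5 = 4.
- If it does not: graded 1 + 2 + 1 = 4, ungraded 9 − 4 = 5.
- Among the 2 × 3 = 6 combinations with some treatment, 3 are ungraded on the first reading and 4 on the second.
- No combination matches two grades.

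**Step 4: sensitivity to the grid.** Splitting mild from moderate limitation gives 4 × 3 = 12 combinations. Graded are 1 + 4 + 2 = 7 or 1 + 4 + 1 = 6, which leaves 5 or 6 ungraded. The gap remains under each definition tried. These are counts of definitions, not of expected events.

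**The case against.** A reader might infer that life-threatening events will be hidden. The documents do not support that. Such an event meets an SAE criterion in Section 11.2 and must reach the sponsor within 24 hours under Section 11.3. It is followed for severity and outcome, and it is counted under seriousness in Section 14.2. With up to 30 subjects it would be noticed. Deaths are likewise captured, both as an SAE criterion and as an outcome, so the lack of a fatal row in Table 1 matters little. This objection stands against any claim of concealment. It does not restore the split between grades 3 and 4 in the severity summary.

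A reader might also infer that the ungraded combinations are common, or that treated events will be misgraded. Neither follows. The documents give no adverse event frequencies. Table 1 applies only where the modified CTCAE criteria are silent, and those criteria cannot be seen here, so the share of events that reach Table 1 is unknown and may be small. Where no row matches, the text assigns no grade at all, so the risk is inconsistency. Section 11.1 also calls the rows guidelines, so reading them as strict joint conditions is a choice. Even on a looser reading, nothing says which part governs.

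Finally, the CRF may already hold four levels, since Section 9.1.06 leaves this open. If so, item 1 of the 11.1 list contradicts the CRF and the text still needs correcting.

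**Conclusion.** The point holds as a reporting inconsistency of low severity. Section 11.1 stores three severity levels while its own Table 1 assigns four, and no rule connects them. On the recorded list as written, which covers all adverse events, the Section 14.2 severity summary cannot show life-threatening events separately from severe ones.

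The Table 1 gap is secondary. It covers 4 of 9 combinations, or 5 of 9 on the narrower reading of required therapy, and applies only to events outside the modified CTCAE criteria. Its practical size cannot be estimated from the documents.

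The conclusion assumes that the CRF follows item 1 of the 11.1 list and, for the count, that both parts of a Table 1 row must be met. The primary PGWB analysis is not affected.

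**What to change.** 1. In item 1 of the 11.1 list and in the CRF code list, carry every grade of the scale in use, with life-threatening as its own value. Do this before data entry.
2. In Section 14.2, state that adverse events are tabulated by those grades.
3. In Table 1, define minimal intervention and have the sponsor state one rule for events whose limitation and intervention point to different rows. Simply taking the worse of the two needs care. On the present wording, an event with no activity limitation that needs more than minimal therapy would become severe, which fits poorly with the section's own statement that severe measures intensity.
4. A separate row for fatal events is optional, because death is already captured elsewhere.

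The cost is a few lines of protocol text, one more code-list value and slightly sparser cells in the severity table.

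### Table 2 lets known toxicity alone qualify an adverse event as definitely related, so known reactions can be over-attributed and can also fit the Possibly row

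*Combined protocol and SAP*

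**What the plan says.** Table 2 (Section 11.1) has four rows: Definitely, Probably, Possibly and Unrelated.

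- **Definitely** begins "Previously known toxicity of agent; or an event that follows a reasonable temporal sequence from administration of the drug". It goes on to require an expected response pattern and confirmation on stopping or reducing the drug, and ends "and that is not explained by any other reasonable hypothesis".
- **Probably** asks for timing, pattern and the same dechallenge confirmation, and for an event "that is unlikely to be explained by the known characteristics of the subject's clinical state or by other interventions".
- **Possibly** asks for timing and for an event "that follows a known or expected response pattern to that suspected drug"; its closing condition reads "but that could readily have been produced by a number of other factors".
- **Unrelated** demands certainty that the drug played no part.

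Nothing says which row prevails when two fit, and known toxicity is not defined. The list of database items earlier in Section 11.1 asks for a two-level rating instead, suspected or not suspected, and no mapping between the scales is given. Section 14.2 summarises adverse events by "body system, severity, seriousness, and relationship to study treatment" without saying which scale it uses.

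**The concern.** In the Definitely row, the conditions on timing, pattern, dechallenge and absence of another explanation are clauses that modify the event named after the *or*. The known-toxicity route before the *or* carries none of them. That the drug can cause a reaction is then taken as proof that it caused this one.

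Safety is a listed secondary endpoint (Section 5.2), and every subject receives dupilumab (Section 4.1). No control rate is available against which to set the investigator's attribution. Competing causes are also to be expected, since Section 7.1 lets topical steroids, phototherapy and other systemic agents continue. Two raters who start from different rows could class the same known reaction as Definitely and as Possibly, and both would be following the table.

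**Working it through.** The plan gives no figure to reproduce, so the check is logical. Take an event that is a known toxicity and assume that this satisfies the response-pattern condition. Three features from Table 2 remain: reasonable timing (yes/no), dechallenge confirmed (yes/no), and other causes (none reasonable / unlikely / could readily explain it). That gives 2 × 2 × 3 = 12 profiles. Where an event meets both the strict and the looser alternative-cause condition of Definitely and Probably, only the higher row is shown.

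| Timing | Dechallenge | Other causes | Rows met as written | Clause simply deleted | Reworded as under the fix |
|---|---|---|---|---|---|
| yes | yes | none | Definitely | Definitely | Definitely |
| yes | yes | unlikely | Definitely and Probably | Probably | Probably |
| yes | yes | readily | Definitely and Possibly | Possibly | Possibly |
| yes | no | none | Definitely | no row | Definitely |
| yes | no | unlikely | Definitely | no row | Probably |
| yes | no | readily | Definitely and Possibly | Possibly | Possibly |
| no | either | any (6 profiles) | Definitely | no related row | explicit lower row |

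**As written.** All 12 of 12 profiles rate Definitely. Of these, 6 lack reasonable timing (2 × 3), and in 4 other factors could readily explain the event (2 × 2). Two profiles meet Definitely and Possibly together: those with reasonable timing and a ready alternative, with or without dechallenge.

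**Strained parse.** Suppose instead that the later conditions govern both routes, so that known toxicity replaces only timing. Then 2 of 12 rate Definitely, 1 of them without reasonable timing, and the overlap with Possibly disappears. The timing gap remains.

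**Clause deleted.** Only 1 + 1 + 2 = 4 profiles have a related row (Definitely, Probably, Possibly). The other 8 are the 6 without reasonable timing, which could be placed only if Unrelated can be certified, and 2 with good timing, no dechallenge and no ready alternative. Those 2 fail Definitely and Probably for want of dechallenge, fail Possibly for want of a competing cause, and are not certainly unrelated. Section 8.3 sets a fixed schedule to week 50 with no dose-reduction step, so events without dechallenge are to be expected.

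**Reworded.** With reasonable timing, 2 + 2 + 2 = 6 profiles fall one row each, and the other 6 go to the lower row. All 12 are placed and none fits two rows.

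These are counts of logical profiles, not event frequencies.

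**The case against.** The strongest reply is that the consequences are small and may vanish. The two-level item may be the one tabulated. If so, Definitely and Possibly would presumably both become suspected, and the overlap would change nothing. That stands for the overlap, though the mapping is an assumption. It does not dispose of the other part: a known reaction that would otherwise be rated not suspected could still be pulled into suspected.

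A reader might infer that timing plays no part at all. The documents do not support that. The adverse event definition already requires an event to be "temporally associated with the use of a medicinal (investigational) product", though this is looser than a reasonable temporal sequence. Dosing runs to week 50 and event capture to week 52 (Section 9.1.06), so onset long after the last dose is largely confined to subjects who stop early and keep attending (Section 12.1).

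A reader might also infer that every event with a known term is misclassified. That is wrong too, because an event meeting all the conditions rates Definitely by either route.

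Serious events are less exposed. Section 11.2 requires reporting irrespective of causality from consent until four weeks after participation ends. Only later reporting turns on the investigator's attribution, and there the clause errs towards reporting.

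**Conclusion.** The point holds as a wording error in a safety classification. Known toxicity is sufficient by itself for Definitely, the row can coincide with Possibly, and no rule settles the tie. Applied as written, the table biases the relatedness summary towards attribution to the drug.

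The size cannot be stated. A percentage could be had only by assumption: if 20% to 60% of events were known reactions, and 10% to 50% of those had another explanation or implausible timing, the product would run from 0.20 × 0.10 = 2% to 0.60 × 0.50 = 30% of events. Nothing in the documents supports either input, so that range should not be cited as an estimate.

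The effect is confined to the tabulation by relationship in a study of up to 30 subjects. The PGWB analysis at Week 16 is untouched, as are the summaries by body system, severity and seriousness. The conclusion rests on the plain punctuation of the row and on raters applying it literally.

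**What to change.** Do not simply delete the clause. Reword Table 2 as follows:

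1. Require reasonable timing for every related class.
2. Let known toxicity stand in only for the response-pattern and dechallenge conditions.
3. For known reactions, let the alternative-cause condition alone separate the classes: Definitely if there is no other reasonable explanation, Probably if another is unlikely, Possibly if other factors could readily explain the event.
4. Assign events without reasonable timing to an explicit lower row.
5. Record expected/unexpected as a separate item.
6. State how the four levels map to the suspected/not suspected item in Section 11.1.

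The cost is a short edit to the table and the CRF guide, and some events will move to a lower class. The edit settles known reactions only. An event with an expected pattern that is not a known toxicity, with good timing, no dechallenge and no ready alternative, still has no row and needs separate attention.
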